### 3.3 Consent and information for participants

In each site we will conduct active case finding activities in collaboration with Ministry of Health departments and National Yaws Programmes. For sub-studies 1-3, all residents in selected communities will be eligible to participate in the study. Prior to any study procedures, written informed consent will be obtained from participants or, from parents, guardians, or legal

representatives if the participant is under the age of consent. Following national recommendations informed consent will be conducted in English or French, with the assistance of a community representative translating if necessary. If a person is illiterate the study information and consent procedure will be clearly explained to them by a member of the study team or a local translator. If a translator is used they will be required to witness the informed consent procedure. Children and minors over ten years of age and under the age of consent, will also be required to give verbal assent for enrolment. If consent is not given for future research, it will be indicated under the appropriate section in the consent form. If any participants wishes to withdraw from the study at any point post-enrolment this will be indicated to study coordinator and data managers for complete elimination of that participants information. Consent forms, approved by all relevant ethical review boards, will be available in English and French, as appropriate. Individuals at each site will be consented for participation into each sub-study based on the relevant inclusion/exclusion criteria (see sections: 4.2; 5.2; 6.2; 7.2).

## 4 SUB-STUDY 1: MULTI-COUNTRY CASE SEARCHES AND EPIDEMIOLOGICAL ANALYSIS OF RISK FACTORS FOR YAWS

### 4.1 Objectives

- 1) Determine the prevalence of active and latent yaws in each setting using combined clinical, serological and molecular tools
- 2) Identify risk factors associated with active and latent yaws
- 3) Collect a representative dried blood spot sample library for future serological testing

We will undertake integrated case searches for individuals with yaws-like lesions. We will collect baseline clinical, demographic and risk factor information from participants. Individuals with clinical evidence of yaws will be tested with point-of-care serological tests (SD Bioline and Chembio DPP) in line with standard WHO recommendations, and will have lesion samples collected which will form the sample set required for sub-studies 2 & 3. We may record the presence of other skin conditions seen.

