## 2 BACKGROUND AND RATIONALE

### 2.1 Background

#### 2.1.1 Yaws

Yaws is a chronic infectious disease of the skin, bone and cartilage caused by the spirochete bacterium *Treponema pallidum* subsp. *pertenue* (TPE). TPE is closely related to the syphilis-causing bacterium *Treponema pallidum* subsp. *pallidum* but unlike syphilis, yaws primarily affects children and is generally not sexually transmitted. It is one of the World Health Organization (WHO) neglected tropical diseases (NTDs) and under the WHO's new roadmap is targeted for eradication by 2030^6. Yaws presents initially as a bacteria-rich papilloma, which if left untreated, can ulcerate. In some cases, the disease progresses to secondary yaws and it is at this stage that it can cause further skin manifestations as well as inflammation of bones and joints. In rare cases tertiary yaws develops; this is often characterised by destructive and disfiguring lesions. Untreated patients are susceptible to developing a latent infection, which can relapse, commonly within five years of the initial infection. During the latent stage of the disease there are no clinical manifestations. It is thought that for every clinical case of yaws there are six latent cases, which has serious implications for eradication programs.

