### **2.1.3 Diagnostics**

Accurately diagnosing yaws will be key to the success of the global eradication campaign.

Traditionally, serological tests have been the mainstay of yaws diagnosis, consisting of detection of treponemal and non-treponemal antibodies. Anti-treponemal antibodies are long-lived so are useful for indicating exposure but cannot distinguish between current and past infections, nor can they distinguish between infection with any of the *T. pallidum* subsp. *pallidum* (syphilis), *pertenue* (yaws), *endemicum* (bejel) or *T. carateum* (pinta). Non-treponemal tests are used to predict a current infection, but lack specificity. When used in conjunction non-treponemal and treponemal tests are a better indicator of a current treponemal infection, but also fail to distinguish between different species of Treponemes, and have been shown to miss early cases of yaws, which could be important for identifying resurgence of the disease after MDA.

Clinical diagnosis based on lesions alone is unreliable, often due to the presence of co-endemic ulcer-causing diseases. Recent studies using molecular tools have demonstrated only one third of yaws-like ulcers are positive for *T. pallidum*. Studies from Papua New Guinea and Solomon Islands have shown *H. ducreyi*, the causative agent of chancroid, to be responsible for a further third of these clinically-indistinguishable lesions. Often neither *T. pallidum* nor *H. ducreyi* are detected in these lesions and it is possible another infectious agent is responsible. Therefore, we will conduct further investigations to determine if other pathogens may be routinely detected that could influence the design of yaws eradication programs.

The urgent need for novel diagnostics is perhaps most essential in light of the emergence of azithromycin-resistant TPE. These strains have been shown to emerge independently, and have led to localized transmission. Highly sensitive and specific nucleic acid amplification tests (NAATs) which include tests for azithromycin resistance are available. However, these tests are often inaccessible and have limited use in the field setting. In light of this emerging macrolide resistance it is clear that more robust laboratory-based surveillance is required.

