### 4.3 Sample Size Considerations

We aim to screen approximately 60,000 individuals, 20,000 in each country. Of these we estimate 6000 individuals will present with yaws like lesions and 600 will have active yaws (i.e. present with yaw-like lesions and confirmed serologically). The remaining participants will be classed as either negative for yaws due to the absence of clinical signs or negative serology or suspected latent yaws if sero-reactive. We will aim to enrol all 6000 participants with yaws like lesions and a further 6000 without clinical yaws into this sub study. This will give us >80% power to detect risk factors associated with yaws with an odds ratio of 3. If resources allow, we will collect dried blood spots of half of the people enrolled into sub-study 1 giving us roughly 6000 dried blood spots samples. This would allow us to detect 5% seroprevalence with 0.5% precision, and a seroprevalence of 50% with a precision of 1.3%, which is deemed more than sufficient for a convenience sample .

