#### **4.5 Sample collection and storage**

As per WHO recommendations, people with clinically suspected yaws lesions will be screened using a *T. pallidum* POC test, and those that test positive will be confirmed with the DPP Screen and Confirm POC test detecting both treponemal and non-treponemal antibodies. In individuals with a positive DPP assay, we will collect lesion swabs for molecular testing according to WHO procedure  (Appendix C). As some cases of yaws occur in individuals who have not yet sero-converted we will also collect swabs from 1/10 people with suspected yaws but non-reactive serological tests. Two swab samples will be simultaneously obtained from each suspected yaws lesion (i.e. rolling both swabs over the lesion at the same time); one to conduct the TPHD-LAMP assay at the district level hospital, the other for PCR at the national reference laboratory for the detection of *T. pallidum* and *H. ducreyi* and monitoring resistance to antibiotics. A maximum of three other swabs may be taken, from the same or different lesions from people with or without yaws, and further swabs may be collected from asymptomatic skin or from fomites in the house, for additional infection detection analysis. Swab samples will be collected dry, or in suitable transport medium, and all tubes will be labelled with the participant's unique identification numbers and collection date. Half of those enrolled into sub-study 1 will be asked to provide a dried blood spot sample. This will give us an archive of around 6000 dried blood spots with which we can perform serological testing in the future. For this we will collect capillary finger blood onto a filter

paper designed specifically for blood collection following published procedures (see Appendix D). These will be air dried for at least 12 hours prior to being stored with desiccant sachets at ambient temperature.

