#### **4.6 Laboratory testing**

The dried blood spots will be used to conduct multiplex serological assays on the Luminex platform to look for antibodies to Treponemes and other infectious diseases. By measuring levels of anti-Treponemal antibodies in children we will be able to estimate the number of latent yaws cases within the community. We will choose a panel of infectious diseases that we know, or suspect, to be endemic in our populations and measure antibody responses specific to these pathogens in order to indicate exposure and seroprevalence at the individual, community and district level .

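### The latent-yaws half of sub-study 1 objectives 1 and 2 is not supported as written: the blood-spot result would measure treponemal exposure, and no latent outcome is modelled

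*Combined protocol and SAP*

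**What the plan says.** Two of the three objectives of sub-study 1 name latent yaws (section 4.1): "Determine the prevalence of active and latent yaws in each setting using combined clinical, serological and molecular tools", and "Identify risk factors associated with active and latent yaws". Section 2.1.1 describes that state: "During the latent stage of the disease there are no clinical manifestations".

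On testing, section 4.5 says that "people with clinically suspected yaws lesions will be screened using a" treponemal point-of-care test, with positives going on to the DPP. Sections 1.3, 3.1 and 4.1 limit point-of-care serology in the same way. Section 4.3 defines active yaws as lesions plus serological confirmation, and places some of the remaining participants in a class of "suspected latent yaws if sero-reactive".

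Lesion-free people are to have dried blood spots as part of a half-sample of sub-study 1. Sections 1.3 and 4.3 make this subject to resources; section 4.5 states it without that condition. Section 4.6 gives the intended use: "By measuring levels of anti-Treponemal antibodies in children we will be able to estimate the number of latent yaws cases within the community". Section 2.1.3 states the limit of that marker: "Anti-treponemal antibodies are long-lived so are useful for indicating exposure but cannot distinguish between current and past infections". It assigns the prediction of current infection to non-treponemal tests.

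Section 4.8 plans logistic regression with odds ratios for active yaws. For the Luminex data it plans cut-offs and seroprevalence with 95% confidence intervals.

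**The concern.** Latent infection has to be looked for in people without lesions, and the plan gives those people only one kind of serology. The marker named for the latent estimate is the one that the background section says cannot do this job. A past, treated or resolved infection in a lesion-free child would be counted as a latent case.

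At stake is what the study can report about latent infection, which section 2.1.1 treats as a serious matter for eradication programmes. A figure labelled latent yaws that really measures exposure would mislead those programmes. The risk-factor objective has a separate gap: its latent half has no case definition, no outcome variable and no model.

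**Working it through.** **1. The plan's own precision figure.** Section 4.3 claims precision of 0.5% at 5% seroprevalence and 1.3% at 50%, from about 6,000 spots. The half-width is 1.96 × √(p(1 − p)/n).
- p = 0.05: 1.96 × √(0.05 × 0.95/6,000) = 0.55 points. The stated 0.5 is this figure cut to one decimal.
- p = 0.50: 1.96 × √(0.50 × 0.50/6,000) = 1.27 points, which matches.

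These figures describe seroprevalence over all spots, all ages, with and without lesions. If half the spots come from lesion-free people (assumption; the split is not stated), n = 3,000 and the half-width at 5% is 0.78 points. The number of children is not given. Sampling error is small either way; the difficulty is what the marker measures.

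**2. Who can be found to be latent.**
- Latent means no clinical signs (2.1.1), so the target group is lesion-free people.
- Point-of-care serology, including the non-treponemal line of the DPP, is for people with lesions (1.3, 3.1, 4.1, 4.5).
- For lesion-free people this leaves the blood spot (4.3, 4.5), read for anti-treponemal antibodies (4.6). No non-treponemal assay is named for it.

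**3. What the blood-spot estimate contains.** Let L be the share of lesion-free children with latent infection and s the share with past infection only. With a perfect assay, a treponemal-only result reads L + s. It equals L only if s = 0, and otherwise overstates it by the factor (L + s)/L. The result is therefore an upper bound on L. A larger n narrows the interval around L + s and leaves s in place.

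**4. Can the factor be computed?** It needs both L and s.
- L: section 2.1.1 cites six latent cases per clinical case. Taking the 600 active cases in 4.3, 6 × 600 = 3,600, and 3,600/54,000 lesion-free people = 6.7%. Taking the 210 qPCR-positive cases expected in 5.3, 6 × 210 = 1,260, and 1,260/54,000 = 2.3%. Both are for all ages, not children.
- s: not in the documents. Assumed here at 0% to 20%.

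| Assumed s | Reads, if L = 6.7% | Factor | Reads, if L = 2.3% | Factor |
|---|---|---|---|---|
| 0% | 6.7% | 1.0 | 2.3% | 1.0 |
| 2% | 8.7% | 1.3 | 4.3% | 1.9 |
| 5% | 11.7% | 1.75 | 7.3% | 3.1 |
| 10% | 16.7% | 2.5 | 12.3% | 5.3 |
| 20% | 26.7% | 4.0 | 22.3% | 9.6 |

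The factor runs from 1.0 to 9.6 purely on the choice of inputs. The documents fix its direction and not its size.

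**5. The risk-factor half.** Section 4.8 models active yaws. It has no latent definition and no latent outcome. The power statement in 4.3 (above 80% for an odds ratio of 3) can be met for active yaws. With 600 cases against 6,000 lesion-free people, two-sided 5%, and the normal approximation with pooled null variance, power is 93% at 1% exposure among the lesion-free and at least 99% from 2% to 95%. This ignores clustering. No corresponding statement for latent yaws can be made.

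**6. From sample to community.** Enrolment is 6,000 with lesions and 6,000 without, or 50/50. Among those screened the expected split is 6,000 and 54,000, or 10/90. The sampling fractions are 6,000/6,000 = 1 and 6,000/54,000 = 1/9, so each lesion-free enrolee stands for nine people. No weighting is described.

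**The case against.** Several points limit how far this goes.

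- *A reader might infer that the latent class in 4.3 is empty.* The documents do not establish that. Section 4.3 does not tie sero-reactive to the point-of-care tests, so blood-spot results could fill the class. Section 1.3 also provides for lesion patients who are positive on the first test but not dual-positive on the DPP; they are sero-reactive without being confirmed active. Objective 1 brings in molecular results as well. At the 35% qPCR positivity assumed in 5.3, 600 − 210 = 390 dual-seropositive patients would be qPCR-negative for *T. pallidum*, and some might be regarded as latently infected with another cause of the lesion. No such rule is written, and people with lesions cannot supply latent prevalence among those without.
- *A reader might infer that latent yaws cannot be obtained at all.* Section 4.6 leaves the antibody panel open and 4.8 leaves the tools open. A non-treponemal marker is not planned, but it is not excluded.
- *Using children limits accumulated past infection.* This stands in part. Section 2.1.1 says that yaws affects mainly children, so children too can carry antibody from a past infection. No age limit or correction is given.
- *The archive is already described as showing previous exposure* (1.9, secondary objective 6). That is true, and it supports relabelling; section 4.6 nevertheless claims latent cases.
- *The main aim is the LAMP evaluation.* That is correct, and the assay's accuracy results are untouched.

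What remains is the conflict between 4.6 and 2.1.3, and the missing latent outcome in 4.8.

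**Conclusion.** The point holds for the latent half of objectives 1 and 2 only. As written, the plan would report treponemal exposure in children under the name of latent yaws. That is an upper bound on latent infection, on the assumption that assay error is ignored. The plan would produce no risk-factor analysis for latent yaws.

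A reader might infer that two whole objectives fail. They do not: the active half of each is served by the testing in 4.5 and the model in 4.8. A reader might also take a fold-overstatement from the table above. The documents support none, because the share of past infection is an assumption and the latent prevalence depends on which cases the six-to-one figure is applied to.

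The change should be made. It costs little, and it decides what the study can conclude about latent infection.

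**What to change.** In section 4.1 (objectives 1 and 2), section 4.3 and section 4.6, limit prevalence and risk factors to active yaws. Remove the latent class from 4.3. Report the blood-spot result as *treponemal exposure seroprevalence in lesion-free children*, with the age range stated, and say that it is not an estimate of latent yaws. This costs wording only; the downside is a less ambitious objective.

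Only if a non-treponemal marker proves feasible on the same spots:
- define *probable latent yaws* as dual reactivity in lesion-free people;
- add it as an outcome, with its own model, in 4.8;
- for any community figure, weight the roughly 50/50 enrolment back to the expected 10/90 among those screened;
- state that dual reactivity reduces misclassification without removing it, since 2.1.3 describes non-treponemal tests as not specific and the combination only as a better indicator.

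The documents do not give the cost or feasibility of that marker, and in 1.3 and 4.3 the spots themselves remain subject to resources. The second option should therefore be an addition to the first and not a replacement for it.

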### 4.2 Inclusion and exclusion criteria

#### Inclusion Criteria

- Resident in selected community
- Willingness to provide informed consent to participate in the study

#### Exclusion Criteria

- Refusal of village chief (for village inclusion), or refusal of individual and/or guardian (for individual inclusion)
- Not willing or able to give informed consent for the study
- Permanent disability that prevents or impedes study participation and/or comprehension

### 4.3 Sample Size Considerations

We aim to screen approximately 60,000 individuals, 20,000 in each country. Of these we estimate 6000 individuals will present with yaws like lesions and 600 will have active yaws (i.e. present with yaw-like lesions and confirmed serologically). The remaining participants will be classed as either negative for yaws due to the absence of clinical signs or negative serology or suspected latent yaws if sero-reactive. We will aim to enrol all 6000 participants with yaws like lesions and a further 6000 without clinical yaws into this sub study. This will give us >80% power to detect risk factors associated with yaws with an odds ratio of 3. If resources allow, we will collect dried blood spots of half of the people enrolled into sub-study 1 giving us roughly 6000 dried blood spots samples. This would allow us to detect 5% seroprevalence with 0.5% precision, and a seroprevalence of 50% with a precision of 1.3%, which is deemed more than sufficient for a convenience sample .

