## 1.3 Study design:

This study will take place in three sub-Saharan African countries known to be endemic for yaws. We aim to screen approximately 60,000 participants, of all ages. Screened participants will undergo primary clinical examination for yaws-like lesions and will be classed as either suspected yaws or negative for active yaws. A proportion of the yaws free participants ( $\approx 10\%$ ) and all those with suspected yaws ( $\approx 6000$  people) will be invited to answer a questionnaire relating to household demographics and possible risk factors for yaws. If resources allow they will also be asked to provide dried blood spots for future serological analysis of yaws and other co-endemic neglected tropical diseases. Rapid point of care (POC) serological tests will then be used to confirm the clinical yaws diagnosis in the field, to allow for recruitment into the diagnostic evaluation study. Those with suspected yaws lesions will be tested with the SD Bioline syphilis test and those who test positive will be confirmed with the Chembio Dual Path Platform Syphilis Screen and Confirm POC test (herein DPP). As some cases of yaws occur in individuals who have not yet sero-converted, in order to improve the *Treponema pallidum pertenue* (TPE) prevalence estimate accuracy, we will collect lesion samples from all individuals with a dual seropositive DPP (treponemal and non-treponemal) and a subsample of the participants (1/10) negative for the SD Bioline or the DPP (either treponemal antibodies, non-treponemal antibodies or both). Two swabs, collected simultaneously from the same lesion, will be used for the diagnostic evaluation of the *T. pallidum* and *Haemophilus ducreyi* Loop-mediated isothermal amplification (TPHD LAMP) assay. Up to three further swabs may be collected from the same or additional lesions of the participant and from individuals with non-seroreactive tests but yaws-like lesions. We will also collect swabs of asymptomatic skin and of fomites of the house from some participants with and without yaws. These additional swabs will allow us to investigate other pathogenic causes of lesions using specific nucleic acid amplification tests and next generation sequencing. We will also be able to perform supplementary laboratory analysis on swab collection and DNA extraction methodologies, investigate the role fomites may have in the transmission of TPE and *H. ducreyi* and further understand the role of *H. ducreyi* as a cause of skin ulcers. No more than five lesion

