### 3.2 Study Sites

In each of the three countries, national reporting data will be used to select at least three districts that are highly endemic for yaws, facilitating rapid fulfilment of the sample size required number of yaws cases for the diagnostic accuracy study. The number of villages/communities selected will depend on prevalence of the disease. This exercise will be conducted with the yaws programme national coordinators in the three endemic countries.

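### The dried-blood-spot precision in section 4.3 is a pooled simple-random-sample margin and is not the precision the design gives for community, district or latent-yaws estimates

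*Combined protocol and SAP*

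**What the plan says.** Section 4.3 expects roughly 6,000 spots, from half of the people enrolled in sub-study 1, and states: "This would allow us to detect 5% seroprevalence with 0.5% precision, and a seroprevalence of 50% with a precision of 1.3" (the last figure is also a percentage). It adds: "which is deemed more than sufficient for a convenience sample". No design effect is given.

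On who the donors are:

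- Section 4.3 on enrolment: "We will aim to enrol all 6000 participants with yaws like lesions and a further 6000 without clinical yaws into this sub study". Section 1.3 describes the second group as "A proportion of the yaws free participants", about 10%.
- Section 4.5 on spots: "Half of those enrolled into sub-study 1 will be asked to provide a dried blood spot sample". Section 1.3 makes this conditional: "If resources allow they will also be asked to provide dried blood spots for future serological analysis". Sections 4.3 to 4.5 do not say how the lesion-free enrollees or the donor half are chosen.
- Section 3.2 on sites: "The number of villages/communities selected will depend on prevalence of the disease". Under section 4.2 a chief's refusal removes a whole village.

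On purpose, section 4.1 lists as an objective: "Collect a representative dried blood spot sample library for future serological testing". Its first objective includes the prevalence of latent yaws. Section 4.6 plans to estimate latent cases in the community from antibodies in children, and to report seroprevalence down to community and district. Section 4.8 sets antibody cut-offs and then calculates seroprevalence with 95% intervals. Its reference to appropriate tools concerns the cut-offs. It mentions neither sampling weights nor clustering.

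**The concern.** A stated margin should describe how far an estimate may fall from its target under the sampling actually used. Three features of this design are missing from the figure in section 4.3. People with lesions are enrolled at a far higher rate than others. People are recruited in villages, where infection status is likely to be correlated. The uses named in section 4.6 are narrower than one sample pooled over three countries.

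The spots matter for one stated aim. Latent yaws has no clinical signs (section 2.1.1), and point-of-care serology is planned only for suspected cases (sections 3.1 and 4.5). The spots are therefore the only serology described for people without lesions. If donors over-represent lesion patients and the results are pooled without weights, a community estimate could be wrong by more than the quoted margin. That could not be repaired later unless screened and donor counts had been kept.

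**Working it through.** **Inputs.** Screened 60,000, of whom 6,000 with lesions and so 54,000 without; enrolled 6,000 and 6,000; spots about 6,000 (all section 4.3). Confidence 95% (section 4.8). Three districts per country (section 1.4), at least three (section 3.2), so nine or more. The donor mix, village sizes and intracluster correlation are not given.

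**1. The plan's own figure.** Half-width = 1.96 × √(p(1−p)/n), n = 6,000.

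- p = 5%: 1.96 × √(0.0475/6,000) = 0.55 points (printed as 0.5, which is 0.55 cut to one decimal).
- p = 50%: 1.96 × √(0.25/6,000) = 1.27 points (printed as 1.3).

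The printed pair is the simple-random-sample margin for all spots pooled.

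**2. Enrolment fractions.** With lesions: 6,000/6,000 = 1. Without: 6,000/54,000 = 1/9, or 11.1%, close to the 10% in section 1.3. Lesion patients are 50% of enrolment but 10% of those screened.

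**3. Pooled estimate weighted to the screened population.** With n1 donors with lesions and n0 without, at seroprevalences p1 and p0:

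Variance = 0.1² × p1(1−p1)/n1 + 0.9² × p0(1−p0)/n0.

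Taking p1 = p0, the effective sample size is 1/(0.01/n1 + 0.81/n0).

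| Lesion share of donors | n1 / n0 | Effective n | Half-width at 5% | Half-width at 50% |
|---|---|---|---|---|
| 50% | 3,000 / 3,000 | 3,659 | 0.71 | 1.62 |
| 25% | 1,500 / 4,500 | 5,357 | 0.58 | 1.34 |
| 10% | 600 / 5,400 | 6,000 | 0.55 | 1.27 |

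At 50:50 the variance inflation is 6,000/3,659 = 1.64.

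**4. Bias if pooled without weights.** With lesion share f among donors, the crude estimate is f × p1 + (1−f) × p0 and the target is 0.1 × p1 + 0.9 × p0. The difference is (f − 0.1)(p1 − p0). At f = 0.5 this is 0.4 × (p1 − p0), which passes 0.5 points when p1 − p0 exceeds 0.5/0.4 = 1.25 points. At f = 0.1 it is zero.

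An illustration from the protocol's figures: p1 = 600/6,000 = 10% (section 1.5). Six latent cases per clinical case (section 2.1.1) gives 3,600; if all are lesion-free, p0 = 3,600/54,000 = 6.7%. The crude value at 50:50 is (10 + 6.7)/2 = 8.3%. The weighted value is 0.1 × 10 + 0.9 × 6.7 = 7.0%. The bias is 1.3 points. This stands a point-of-care result in for the later antibody assay, so it shows scale only.

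**5. Clustering.** Every half-width is multiplied by the square root of a design effect, 1 + (m − 1) × ICC, for m spots per village. Both inputs are assumptions. Combined with the 1.64 from step 3:

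- m = 20, ICC = 0.01: 1.19 × 1.64 = 1.95, half-widths 0.77 and 1.77 points.
- m = 100, ICC = 0.05: 5.95 × 1.64 = 9.76, half-widths 1.72 and 3.95 points.

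**6. District estimates.** With nine districts and an even spread (assumed), 6,000/9 ≈ 667 spots each. 1.96 × √(0.0475/667) = 1.7 points and 1.96 × √(0.25/667) = 3.8 points, before weighting or clustering.

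**7. Latent yaws.** This needs lesion-free children. At a 50:50 mix there are about 3,000 lesion-free donors of all ages, so the number of children is smaller by an amount the plan does not give.

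**The case against.** There is no slip of arithmetic: the printed figures reproduce. The size of the effect depends on a donor mix the plan leaves open. If a tenth of donors have lesions, neither bias nor loss from weighting arises, and at a quarter the weighted margin is almost as printed. Section 4.8 does not commit to a crude pooled estimate; it is silent. Section 4.3 calls the spots a convenience sample, collection depends on resources, the archive is a secondary objective in section 1.9, and no decision rule hangs on the margin. Weighting by sampling fractions also presumes near-random selection within lesion strata, which a convenience sample may not offer.

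Most of this stands, and it limits the size and shapes the remedy. It does not rescue the figure. A convenience label does not support a random-sampling margin, and it conflicts with the representative library in section 4.1. Even in the most favourable donor mix, village clustering and the move to district level or to children remain unaddressed.

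A reader might infer that 3,000 lesion-free donors, with margins of 0.78 and 1.79 points by the formula in step 1, give the latent-yaws precision. They do not, because section 4.6 bases that estimate on children. Nor do 0.7 and 1.6 points describe a community or district; they are pooled over three countries.

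**Conclusion.** The point holds, as something the sponsor should correct. Four things are plain from the documents: the margin in section 4.3 is the pooled simple-random-sample value; enrolment is at fractions of 1 and about 1/9 within recruited villages; section 4.8 plans no weighting or clustering; and sections 4.1 and 4.3 describe the sample in conflicting terms. The margin is therefore not the precision for the uses named in section 4.6.

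The size is conditional. If donors mirror enrolment, which is inferred, the pooled weighted margins at equal seroprevalence in both strata are about 0.7 and 1.6 points before clustering, and the crude bias is 0.4 × (p1 − p0). For antibodies unrelated to lesions there is no such bias, and the crude pooled margin holds apart from clustering. The design effect for clustering is unknown.

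A reader might go further and conclude that the seroprevalence results will be biased, or that 6,000 spots are too few. The documents support neither: the donor mix and the form of the estimate are not stated, and no precision target is set that the wider margins would fail. The LAMP evaluation is unaffected.

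**What to change.** - **Section 4.5:** state how lesion-free enrollees and spot donors are chosen, and keep screened and donor counts by village and lesion status. This should be settled before collection starts.
- **Section 4.8:** report seroprevalence by lesion stratum. Where selection within strata supports it, weight community or district estimates by the sampling fractions, with village-clustered 95% intervals. Otherwise present the results as descriptive of those sampled.
- **Section 4.3:** label the present figures as pooled simple-random-sample values, and restate precision for each intended use with a stated design-effect assumption. The latent-yaws margin should use the expected number of lesion-free children.
- **Sections 4.1 and 4.3:** reconcile the two descriptions of the sample.

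The cost is a written donor rule, a tally by village and lesion status, a little more analysis, and probably a less favourable stated precision. The number of spots need not change.
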